#### 3.2.5 Other Meds:

- 3.2.5.1 Participants who are receiving any other investigational agents.
- 3.2.5.2 Immunosuppressive medications / steroids:
  - Subject must not require high dose systemic corticosteroids defined as dexamethasone  $> 4$  mg/day or bioequivalent for at least 3 consecutive days within 2 weeks prior to Day 1 of study therapy;
  - *Inhaled or topical steroids and adrenal replacement doses  $> 10$  mg daily prednisone equivalents are permitted in the absence of active autoimmune disease.*
  - *Subjects are permitted to use topical, ocular, intra-articular, intranasal, and inhalational corticosteroids (with minimal systemic absorption).*
  - *Physiologic replacement doses of systemic corticosteroids are permitted, even if  $> 10$  mg/day prednisone equivalents.*
  - *A brief course of corticosteroids for prophylaxis (e.g., contrast dye allergy) or for treatment of non-autoimmune conditions (e.g., delayed-type hypersensitivity reaction caused by contact allergen) is permitted.*
- 3.2.5.3 Has received a live vaccine within 30 days prior to the first dose of study drug; seasonal influenza vaccination is permitted excluding the nasal spray formulation;
- 3.2.5.4 No concurrent treatment on another clinical trial. Supportive care trials or non-treatment trials, e.g. quality of life, are allowed;

CONFIDENTIAL

This document is confidential. Do not disclose or use except as authorized.

**3.2.6 Concomitant Medical Illnesses:** Uncontrolled intercurrent illness, including - but not limited to:

- 3.2.6.1 Known additional malignancy that is progressing or requires active treatment within 3 years of start of study drug. Exceptions include basal cell carcinoma of the skin, squamous cell carcinoma of the skin, or *in situ* cervical cancer that has undergone potentially curative therapy;
- 3.2.6.2 Has evidence of interstitial lung disease or active, non-infectious pneumonitis;
- 3.2.6.3 Any serious or uncontrolled medical disorder that, in the opinion of the investigator, may increase the risk associated with study participation or study drug administration, impair the ability of the subject to receive protocol therapy, or interfere with the interpretation of study results examples include but are not limited to symptomatic congestive heart failure, unstable angina pectoris, cardiac arrhythmia or psychiatric illness/social situations that would limit compliance with study requirements;
- 3.2.6.4 Has an active autoimmune disease requiring systemic treatment within the past 3 months or a documented history of clinically severe autoimmune disease, or a syndrome that requires systemic steroids or immunosuppressive agents. Subjects with vitiligo, type 1 diabetes mellitus, residual hypothyroidism due to autoimmune condition requiring hormone replacement, psoriasis not requiring systemic treatment, conditions not expected to recur in the absence of an external trigger or resolved childhood asthma/atopy would be exceptions to this rule. Subjects that require intermittent use of bronchodilators or local steroid injections would not be excluded from the study. Subjects with hypothyroidism stable on hormone replacement or Sjogren's syndrome will not be excluded from the study;
- 3.2.6.5 Has an active infection requiring intravenous therapy;
- 3.2.6.6 Positive test for hepatitis B virus surface antigen (HBV sAg) or detectable hepatitis C virus ribonucleic acid (HCV RNA) indicating acute or chronic infection

**3.2.7 Medical History:**

- 3.2.7.1 History of intracranial abscess within 6 months prior to start of study therapy;
- 3.2.7.2 Known history of testing positive for human immunodeficiency virus (HIV) or known acquired immunodeficiency syndrome (AIDS);  
NOTE: HIV-positive participants on combination antiretroviral therapy are ineligible because of the potential for pharmacokinetic interactions with Nivolumab.  
Appropriate studies will be undertaken in participants receiving combination antiretroviral therapy when indicated.
- 3.2.7.3 History of allergy to study drug components
- 3.2.7.4 History of severe hypersensitivity reaction to any monoclonal antibody;

**3.2.8** Prisoners or participants who are involuntarily incarcerated;

**3.2.9** Pregnant women are excluded from this study because Nivolumab is an agent with the potential for teratogenic or abortifacient effects. Because there is an unknown but potential risk for adverse events in nursing infants secondary to treatment of the mother with Nivolumab, breastfeeding should be discontinued if the mother is treated Nivolumab.

CONFIDENTIAL

This document is confidential. Do not disclose or use except as authorized.

### **3.3 Inclusion of Women and Minorities**

Both men and women of all races and ethnic groups are eligible for this trial.

### **3.4 Women of Childbearing Potential**

A woman of childbearing potential (WOCBP) is defined as any female who has experienced menarche and who has not undergone surgical sterilization (hysterectomy or bilateral oophorectomy) and is not postmenopausal. Menopause is defined as 12 months of amenorrhea in a woman over age 45 years in the absence of other biological or physiological causes. In addition, women under the age of 55 years must have a serum follicle stimulating hormone, (FSH) level  $> 40\text{mIU/mL}$  to confirm menopause.\*

\*Women treated with hormone replacement therapy, (HRT) are likely to have artificially suppressed FSH levels and may require a washout period in order to obtain a physiologic FSH level. The duration of the washout period is a function of the type of HRT used. The duration of the washout period below are suggested guidelines and the investigators should use their judgment in checking serum FSH levels. If the serum FSH level is  $> 40\text{ mIU/ml}$  at any time during the washout period, the woman can be considered postmenopausal:

- 1 week minimum for vaginal hormonal products (rings, creams, gels)
- 4 week minimum for transdermal products
- 8 week minimum for oral products

Other parenteral products may require washout periods as long as 6 months.

## **4. REGISTRATION PROCEDURES**

All sites should e-mail the Study Coordinator at [NeuroOnc\\[contact]](mailto:[contact]) to verify slot availability.

### **4.1 General Guidelines for DF/HCC Institutions**

Institutions will register eligible participants in the Clinical Trials Management System (CTMS) OnCore. Registrations must occur prior to the initiation of protocol-specific therapy or intervention. Any participant not registered to the protocol before protocol-specific therapy or intervention begins will be considered ineligible and registration will be denied.

An investigator will confirm eligibility criteria and a member of the study team will complete the protocol-specific eligibility checklist.

Following registration, participants may begin protocol therapy. Issues that would cause treatment delays should be discussed with the Overall Principal Investigator (PI). If a participant does not receive protocol therapy following registration, the subject must be taken off study in the CTMS (OnCore) with an appropriate date and reason entered.

### **4.2 Registration Process for DF/HCC Institutions**

Applicable DF/HCC policy (REGIST-101) must be followed.

CONFIDENTIAL

This document is confidential. Do not disclose or use except as authorized.

## 5. TREATMENT PLAN

### 5.1 Cohort 1: Nivolumab Monotherapy Treatment Regimen

Nivolumab will be administered every 2 weeks\*, with 14 consecutive days defined as a treatment cycle.

Dosing window\*: There is an administration window of -2/+5 days for Nivolumab administrations; however, participants may be dosed no less than 12 days (11 non-dosing days) between doses.

Labs/assessments window: Labs/assessments may be performed up to 3 days prior to Nivolumab doses.

\* NOTE: Participants who have received active study therapy for  $\geq$  6 months will be allowed the option to adjust their Nivolumab dosing schedule from 240 mg once every 2 weeks (-2/+5 days) to 480 mg once every 4 weeks (+/- 1 week).

Counting of days will not be continuous on study. In the event of a treatment delay due to a toxicity, the current cycle will be extended until the criteria to resume treatment are met. The day of treatment restart will be the participant's subsequent cycle's Day 1.

If treatment with study medication is delayed  $>$  6 weeks, the participant must be permanently discontinued from study therapy, except as specified in Section 6.4.

Treatment will be administered on an outpatient basis. Reported adverse events and potential risks are described in Section 7. Appropriate dose modifications are described in Section 6. No investigational or commercial agents or therapies other than those described below may be administered with the intent to treat the participant's malignancy.

For details regarding drug storage, preparation, administration, and use time please refer to Section 8 of the protocol and the current BMS-936558 (nivolumab) Investigator Brochure.

Nivolumab is to be administered as an IV infusion over 30 minutes (window of -10 / + 30 min). At the end of the infusion, flush the line with a sufficient quantity of normal saline.

#### **Selection and Timing of Dose for Each Participant**

The dosing regimen and schedule of nivolumab are detailed in Table 5.1-1.

Table 5.1-1 Dosing Schedule for Cohort 1					
Cycles = 2 weeks (Nivolumab dosing every 2 weeks) *					
	Cycle 1 Day 1	Cycle 2 Day 1	Cycle 3 Day 1	Cycle 4 Day 1	Cycle 5 Day 1
Nivolumab Dose	240 mg				

\* NOTE: Participants who have received active study therapy for  $\geq$  6 months will be allowed the option to adjust their Nivolumab dosing schedule from 240 mg once every 2 weeks (-2/+5 days) to 480 mg once every 4 weeks (+/- 1 week).

CONFIDENTIAL

This document is confidential. Do not disclose or use except as authorized.

## 5.2 Cohort 2: Nivolumab plus Ipilimumab Treatment Regimen

The dosing regimen and schedule of nivolumab and ipilimumab are detailed in Table 5.2-1. Nivolumab and ipilimumab therapy will start no sooner than 1 week and no later than 12 weeks after completion of radiation therapy. Radiation therapy includes either initial radiation therapy or re-irradiation and can incorporate either conventional conformal dosing or stereotactic radiosurgical dosing based on established, institutional standard of care guidelines. An initial safety lead-in will be performed to determine the maximum tolerated dose (MTD)/recommended phase 2 dose (RP2D) of nivolumab plus ipilimumab following radiation therapy for patients with recurrent/progressive meningioma.

**Table 5.2 Dosing Schedule for Cohort 2**

Treatment Period	Agent	Dose	Frequency	# Planned Doses
Initial combination	Nivolumab	3 mg/kg	Every 3 weeks	4
	Ipilimumab	1 mg/kg	Every 3 weeks	4
Maintenance	Nivolumab	480 mg	Every 4 weeks	Indefinite

### 5.2.1 Safety Lead-In

The safety lead-in will utilize a 3+3 design to determine the MTD/RP2D of ipilimumab when administered with nivolumab following radiation therapy for patients with recurrent/progressive meningioma. Nivolumab will be administered at 3 mg/kg every three weeks with ipilimumab. The initial dose level of ipilimumab will be 1 mg/kg every three weeks and will be administered on the same day as nivolumab. There is extensive existing safety data confirming adequate tolerability of nivolumab administered with ipilimumab at these dose levels. However, since there is no safety data administering these two agents following radiation therapy for recurrent/progressive meningioma patients, the first six patients will be considered a safety lead-in and observed in groups of three for dose limiting toxicities (DLT) for an evaluation period of 42 days (see DLT definitions in Section 5.2.1.1) as follows:

- If at Dose Level 0,  $\leq 1$  of the first 3 patients develop DLT, 3 more patients will be enrolled to Dose Level 0.
- If at Dose Level 0,  $>1$  of the first 3 patients or  $>1$  of the first 6 patients develop DLT, cohort enrollment will be stopped immediately, and re-started from the beginning with 3+3 patients enrolled at a dosing interval of 4 weeks (Dose Level -1).
- If at Dose Level -1,  $>1$  of the first 3 patients or  $>1$  of 6 patients develop DLT, cohort enrollment will be stopped immediately, and re-started from the beginning with 3+3 patients enrolled at a dosing interval of 6 weeks (Dose Level -2).
- If at Dose Level -2,  $>1$  of the first 6 patients develops DLT, the safety lead-in will be discontinued. In this case, a single-arm phase II study of nivolumab monotherapy will be performed.

Dose-limiting toxicities (DLT) will be determined by toxicities related to ipilimumab during or beginning over the first 42 days of treatment as defined below in Section 5.2.2.

Table 5.2.1. Dose levels and doses to be evaluated in safety lead-in.

CONFIDENTIAL

This document is confidential. Do not disclose or use except as authorized.

Dose level	Nivolumab		Ipilimumab	
	Dose (mg/kg)	Frequency	Dose (mg/kg)	Frequency
Zero (0)	3	Every 3 weeks	1	Every 3 weeks
Minus one (-1)	3	Every 4 weeks	1	Every 4 weeks
Minus two (-2)	3	Every 6 weeks	1	Every 6 weeks

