## 1. OBJECTIVES

We hypothesize that inhibition of PD-1 signaling will generate meaningful anti-tumor benefit and will be well tolerated for progressive/recurrent meningioma patients. We propose to initially evaluate Nivolumab in an open-label, phase II study for patients with recurrent atypical or anaplastic meningioma. The study has been amended to include a second cohort (cohort 2) of participants where the combination of nivolumab plus ipilimumab is evaluated following administration of radiation therapy. Enrollment to cohort 2 will commence upon completion of enrollment to the original cohort (cohort 1) of participants treated with nivolumab monotherapy. In addition, the study has been amended to include patients with grade 1 meningioma that have progressed after prior radiation therapy based on the lack of effective therapies for these patients and their decreased outcome.

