### 5.2.2 Definition of Dose-Limiting Toxicity

A DLT is defined as any grade  $\geq 3$  adverse event that is at least possibly, probably or definitely related to ipilimumab during the DLT period, unless judged by the treating Investigator to be more likely related to underlying tumor, concurrent medication or co-morbid event. The DLT period is considered the first 42 days of study therapy and will include labs and other evaluations taken at the end of six weeks of study therapy. Events that are considered unlikely related to ipilimumab, but at least probably related to radiation therapy will not be considered a DLT.

The following exceptions will not be classified as DLT:

- Grade 3 Immune-related adverse events (irAEs – see definition below) that downgrade to Grade  $\leq 2$  within 5 days, or to Grade  $\leq 1$  or baseline within 14 days after onset of the event, whereby maximal supportive care, including systemic corticosteroids, is permitted.
- Grade 3 asymptomatic endocrinopathy, managed with or without systemic corticosteroid therapy and/or hormone replacement therapy.
- Grade 3 inflammatory reaction attributed to a local antitumor response (e.g., inflammatory reaction at sites of metastatic disease, lymph nodes, etc).
- Grade 2 pneumonitis, neurological event, or uveitis that downgrades to Grade  $\leq 1$  within 3 days, whereby maximal supportive care is permitted.
- Liver transaminase elevation  $\leq 8$  times ULN.
- Total bilirubin  $\leq 5$  times ULN.
- Any pre-existing lab abnormality that deteriorates to Grade 3/4, but where the increment of deterioration is considered not clinically significant by Investigator, overall study Principal Investigator and sponsor.

DLT will also include grade 2 immune-related adverse events that occur during the DLT period defined above that require interruption of ipilimumab and do not improve to grade  $\leq 1$  with appropriate supportive care and symptomatic treatment with 7 days.

Immune-related adverse events (irAEs) are defined as AEs of immune nature (i.e., inflammatory) in the absence of a clear alternative etiology. In the absence of clinical abnormality, repeat laboratory testing will be conducted to confirm significant laboratory findings prior to designation as a DLT.

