While rules for adjudicating DLTs are specified above, an AE of Grade  $< 3$  (except if listed as exempt above), may also be defined as a DLT after a consultation with the Sponsor and the overall study Principal Investigator, based on the emerging safety profile of ipilimumab.

Patients who experience DLT may be discontinued from study therapy and will enter the post-study follow-up phase of the study (see Section 5.7) or participants who have fully recovered from

CONFIDENTIAL

This document is confidential. Do not disclose or use except as authorized.

the DLT may proceed with nivolumab monotherapy dosing every 4 weeks if considered appropriate by the treating physician.

Adverse events that meet DLT criteria but occur outside the DLT window will be classified as unacceptable AEs and study treatment will be discontinued per Section 5.6.

For the safety lead-in portion of this study, patients are evaluable for DLTs if: 1) they experience a DLT at any time during the DLT evaluation period; or 2) in the absence of DLT have received at least one dose of ipilimumab and one dose of nivolumab, and have completed respective safety assessments without major violations over the entire DLT evaluation period. Patients who are not fully evaluable for DLTs during the DLT evaluation period of 6 weeks following Day 1, will be replaced.

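### One 42-day DLT window serves three schedules that differ only in dosing interval, so Dose Level -2 is judged on a single combination dose

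*Combined protocol and SAP*

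**What the plan says.** Section 5.2.1 describes a 3+3 lead-in whose patients are "observed in groups of three for dose limiting toxicities (DLT) for an evaluation period of 42 days". Section 5.2.2 repeats the figure: "The DLT period is considered the first 42 days of study therapy". Its evaluability rule says that patients who are not fully evaluable "during the DLT evaluation period of 6 weeks following Day 1, will be replaced". Neither section gives a window specific to a level.

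The starting level is stated as "The initial dose level of ipilimumab will be 1 mg/kg every three weeks", with nivolumab 3 mg/kg on the same day. Table 5.2.1 keeps both mg/kg doses unchanged at Levels -1 and -2 and lengthens the interval to 4 and 6 weeks. The last step is described as "3+3 patients enrolled at a dosing interval of 6 weeks (Dose Level -2".

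For evaluability, Section 5.2.2 requires that patients "in the absence of DLT have received at least one dose of ipilimumab and one dose of nivolumab", and that they complete the safety assessments over the whole period without major violations.

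If more than 1 of 6 patients has a DLT at Level -2, the lead-in stops: "In this case, a single-arm phase II study of nivolumab monotherapy will be performed". Section 1 says: "Enrollment to cohort 2 will commence upon completion of enrollment to the original cohort (cohort 1) of participants treated with nivolumab monotherapy".

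**The concern.** When de-escalation works by spacing doses out, a window fixed in calendar days cuts what is observed along with what is given. At the 6-week interval the second dose falls just outside the window. The level can then be declared acceptable without any repeat dose having been assessed in that decision.

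This matters most at Level -2, which opens only after two denser schedules have failed. Patients enrolled after a pass would go on to repeat doses on that schedule, yet the 3+3 decision would rest on the first dose alone.

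The evaluability rule may weaken the test at any level. One dose of each drug is the only stated minimum exposure, so a patient who misses dose 2 for a reason other than toxicity may be counted as DLT-free.

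**Working it through.** **Inputs.** Window: Days 1 to 42 (Sections 5.2.1 and 5.2.2). Intervals: 21, 28 and 42 days (Table 5.2.1). Pass rule: at most 1 DLT in 6 (Section 5.2.1). Dosing allowance: -2/+5 days (Sections 5.2.3 and 5.2.4). Day 1 is taken as the first combination infusion.

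**The plan's own figure.** 6 weeks × 7 = 42 days, so the three statements of the window agree. 42 days is also exactly two Level 0 intervals (2 × 21). The plan gives no operating characteristics for the lead-in.

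**Dose days.** Dose k falls on Day 1 + (k - 1) × interval.

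| Level | Nominal dose days | Doses in Days 1-42 | Days observed from dose 2 (dose day included) |
|---|---|---|---|
| 0 | 1, 22, 43 | 2 | 42 - 22 + 1 = 21 |
| -1 | 1, 29, 57 | 2 | 42 - 29 + 1 = 14 |
| -2 | 1, 43, 85 | 1 | 0 |

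If the -2 day allowance is used at Level -2, dose 2 falls on Day 41 and is observed for 42 - 41 + 1 = 2 days.

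**Illustrative pass probabilities.** The documents give no DLT risk per dose. Assume a risk p for each dose, independent across doses and unaffected by interval. With k doses in the window, a patient's DLT probability is q = 1 - (1 - p)^k. The pass probability is P(X ≤ 1) = (1 - q)^6 + 6q(1 - q)^5. The early stop for more than 1 DLT in the first 3 does not change this, because such a level fails at 6 as well.

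| p | q, one dose | Pass, one dose | q, two doses | Pass, two doses |
|---|---|---|---|---|
| 0.05 | 0.050 | 0.967 | 0.098 | 0.891 |
| 0.10 | 0.100 | 0.886 | 0.190 | 0.680 |
| 0.20 | 0.200 | 0.655 | 0.360 | 0.301 |
| 0.30 | 0.300 | 0.420 | 0.510 | 0.100 |

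Example, p = 0.20. One dose: 0.8^6 + 6(0.2)(0.8^5) = 0.262 + 0.393 = 0.655. Two doses: 0.64^6 + 6(0.36)(0.64^5) = 0.069 + 0.232 = 0.301.

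**Equal follow-up after dose 2.** With 21 days counted from dose 2, the window ends on Day 22 + 20 = 42 at Level 0, 29 + 20 = 49 at Level -1 and 43 + 20 = 63 at Level -2.

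**A conflict that moves the Level 0 figure.** Section 5.2.4 and the Section 10.2 calendar footnote on ipilimumab require at least 24 days between ipilimumab doses, although the schedule is every 21 days and the allowance extends to 2 days early. Under the 24-day minimum, dose 2 at Level 0 is no earlier than Day 25. Two doses still fall inside 42 days, but 21 days of follow-up would end on Day 25 + 20 = 45.

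**The case against.** **Later toxicity is not ignored.** Section 5.2.2 classes events that meet DLT criteria after the window as unacceptable adverse events, with treatment discontinued. Section 14.1.5.2 suspends cohort accrual on a toxicity threshold at any time. Section 12.2 has the data and safety monitoring committee review toxicity, possibly including DLT information. All of this stands: doses after the first are monitored. None of it enters the 3+3 decision, however, and the Section 14.1.5.2 rule counts only related non-hematologic events of grade 4 or higher, whereas a DLT generally starts at grade 3.

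**A lower DLT count at Level -2 is partly the aim.** Spacing doses out lowers dose intensity and may lower risk. This stands, and it is why the percentages are only illustrative. The difficulty is that the fixed window cannot separate that benefit from the shorter look.

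**Level -2 may never open.** Under the same assumptions, with two doses observed at Levels 0 and -1, it opens with probability (1 - 0.680)² = 0.10 at p = 0.10 and (1 - 0.301)² = 0.49 at p = 0.20. This limits how often the defect bites, but not its effect when it does.

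**Evaluability.** The rule also demands assessments without major violations. Whether a missed dose 2 is a major violation is undefined, so the text is ambiguous; it does not plainly admit such patients.

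**Stronger readings to avoid.** A reader might infer that repeat dosing goes untested at Level -1 too. It does not: two doses fall in the window there. Even at Level -2, patients at the denser levels will already have received the same mg/kg doses. A reader might also cite a four-dose cumulative risk of 1 - 0.8^4 = 59% at p = 0.20. That would apply equally at Level 0 and would remain after the fix, so it does not measure this defect.

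**Conclusion.** The concern holds for Level -2. On nominal days, its dose-level decision rests on one combination dose (with at most 2 days after dose 2 if the early allowance is used), against two doses at Levels 0 and -1. Level -1 is affected only by 7 fewer days after dose 2 (14 against 21). These counts follow directly from the plan's dates and need no assumption about risk.

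The size of the resulting leniency is not known. Over assumed per-dose risks of 10% to 30%, observing one dose rather than two raises the chance of passing by about 21 to 35 percentage points (0.886 - 0.680 = 0.206; 0.655 - 0.301 = 0.354; 0.420 - 0.100 = 0.320). This rests on independent risks that do not change with interval, and so overstates the effect if longer spacing lowers the risk per dose.

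The monotherapy fallback is a separate and smaller point. A reader might infer that it simply repeats Cohort 1, but Section 5.2.1 does not say whether radiation would be kept, so that is not established. What the documents do show is that the fallback is unspecified. Section 1 has Cohort 1 enrollment complete before Cohort 2 opens, and Section 14 sizes two cohorts only. No population, radiation component or analysis is given for a further study.

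**What to change.** 1. In Sections 5.2.1 and 5.2.2, define the DLT window as Cycle 1 Day 1 through the same fixed follow-up after the second combination dose at every level. With 21 days counted from dose 2, this is nominally 42, 49 and 63 days at Levels 0, -1 and -2.
2. In Section 5.2.2, require the second combination dose for DLT evaluability unless it was withheld for toxicity, and replace other patients who miss it.
3. Reconcile the 24-day minimum between ipilimumab doses (Section 5.2.4 and the Section 10.2 footnote) with the every-3-week schedule, because it shifts the Level 0 window by a few days.
4. Reconcile the monotherapy fallback in Section 5.2.1 with Sections 1 and 14, so that its status, population, radiation component and analysis are clear.

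The cost is amendment wording, plus about 1 week (49 - 42 = 7 days) or 3 weeks (63 - 42 = 21 days) more observation per group if Level -1 or -2 opens. The end of the window will also move by some days with dosing allowances or delays, at Level 0 as well, and a patient will occasionally need replacing.

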### **5.2.3 Nivolumab Therapy**

Nivolumab will initially be administered every 3 weeks at a dose of 3 mg/kg for four doses in combination with ipilimumab, and then will be administered at a flat dose of 480 mg every four weeks until study therapy discontinuation.

Dosing window: There is an administration window of -2/+5 days for Nivolumab administrations.

Labs/assessments window: Labs/assessments may be performed up to 7 days prior to Nivolumab doses.

Counting of days will not be continuous on study. In the event of a treatment delay due to a toxicity, the current cycle will be extended until the criteria to resume treatment are met. The day of treatment restart will be the participant's subsequent cycle's Day 1.

If treatment with study medication is delayed > 12 weeks, the participant must be permanently discontinued from study therapy, except as specified in Section 6.4.

Treatment will be administered on an outpatient basis. Reported adverse events and potential risks are described in Section 7. Appropriate dose modifications are described in Section 6. No investigational or commercial agents or therapies other than those described below may be administered with the intent to treat the participant's malignancy.

For details regarding drug storage, preparation, administration, and use time please refer to Section 8 of the protocol and the current BMS-936558 (nivolumab) Investigator Brochure.

Nivolumab is to be administered as an IV infusion over 30 minutes (window of -10 / + 30 min). At the end of the infusion, flush the line with a sufficient quantity of normal saline. On treatment days when both nivolumab and ipilimumab are administered, nivolumab will be administered first with a 30 minute observation window before starting ipilimumab.

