#### 7.2.6 Attribution of the AE:

The causal relationship will be made for each of the agents of study therapy: nivolumab, ipilimumab (when applicable), and radiation (when applicable). Attribution is determined by an appropriately trained and delegated clinician and should be used to assess all adverse events (AE). The causal relationship can be one of the following:

- Definite – The AE is *clearly related* to the study treatment.
- Probable – The AE is *likely related* to the study treatment.
- Possible – The AE *may be related* to the study treatment.
- Unlikely – The AE is *doubtfully related* to the study treatment.
- Unrelated – The AE is *clearly NOT related* to the study treatment.

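### The Cohort 2 lead-in has two different stated aims, and its DLT count omits severe events attributed to nivolumab but not to ipilimumab

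*Combined protocol and SAP*

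**What the plan says.** Two sentences give the aim of the lead-in. Section 5.2 says that it will determine "the maximum tolerated dose (MTD)/recommended phase 2 dose (RP2D) of nivolumab plus ipilimumab following radiation therapy". Section 5.2.1 says: "The safety lead-in will utilize a 3+3 design to determine the MTD/RP2D of ipilimumab when administered with nivolumab following radiation therapy". Section 5.2.1 then justifies the lead-in by the absence of safety data on the two drugs together after radiation in this disease. Table 5.2.1 keeps the mg/kg doses fixed and moves both drugs from every 3 weeks (level 0) to every 4 weeks (level -1) and every 6 weeks (level -2).

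The DLT rule is tied to one drug: "Dose-limiting toxicities (DLT) will be determined by toxicities related to ipilimumab during or beginning over the first 42 days of treatment". Section 5.2.2 defines a DLT as a grade 3 or higher event at least possibly related to ipilimumab, subject to listed exceptions. An event is also removed "unless judged by the treating Investigator to be more likely related to underlying tumor, concurrent medication or co-morbid event". A separate sentence excludes events unlikely to be due to ipilimumab and at least probably due to radiation.

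A patient without a DLT is evaluable only if, among other conditions, they "in the absence of DLT have received at least one dose of ipilimumab and one dose of nivolumab"; patients who are not fully evaluable are replaced. On combination days, "nivolumab will be administered first with a 30 minute observation window before starting ipilimumab" (Section 5.2.3). Section 7.2.6 requires a separate causality rating for nivolumab, ipilimumab and radiation.

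**The concern.** A dose-finding rule should count the toxicity of whatever is being dose-found. Under the Section 5.2 aim that is the two-drug regimen after radiation, and the de-escalation table agrees, since each step spaces out both drugs. The DLT definition agrees only with the narrower aim in Section 5.2.1. Because causality is rated per agent, a severe event can be rated related to nivolumab and unlikely for ipilimumab, and it then has no effect on whether the level is kept.

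The decision rests on six patients and a threshold of one DLT, so a single uncounted event can change the outcome. The rating that decides whether an event counts is an open-label clinical judgment between two checkpoint inhibitors given on the same day.

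**Working it through.** **Routes to a DLT.** There are four statements of what counts, and none reaches an event attributed to nivolumab alone:

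- Summary sentence, Section 5.2.1: related to ipilimumab.
- Grade 3 or higher definition, Section 5.2.2: at least possibly related to ipilimumab.
- Grade 2 immune-related rule, Section 5.2.2: must require interruption of ipilimumab.
- Discretionary rule, Section 5.2.2: only below grade 3, and based on ipilimumab's emerging safety profile.

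**What this does to particular events.**

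- Grade 3 or higher, possibly related to both drugs: counts, unless a listed exception applies.
- Grade 3 or higher, related to nivolumab and unlikely or unrelated to ipilimumab: does not count.
- The same event, also at least probably related to radiation: excluded a second time by the radiation sentence.
- Severe reaction during the first nivolumab infusion: it precedes any ipilimumab, so it cannot be ipilimumab-related and is not a DLT. If ipilimumab is never given, the patient fails the evaluability condition and is replaced, so the event leaves the denominator as well as the numerator.

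**Effect on the 3+3.** The documents give no target DLT rate or operating characteristic for the lead-in, so there is no stated figure to reproduce. Inputs:

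- From Section 5.2.1: 6 patients in two groups of 3; more than 1 DLT in the first 3 or in the 6 fails the level. One or fewer in 6 implies one or fewer in the first 3, so the level is kept exactly when X ≤ 1 of 6.
- Assumed: T, the true rate of DLT-grade toxicity from either drug, and f, the share of those events rated related to nivolumab and unlikely or unrelated to ipilimumab.

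The counted rate is p = T(1 − f), and P(keep) = (1 − p)^6 + 6p(1 − p)^5.

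For T = 40%:

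- f = 0: p = 0.40; 0.0467 + 0.1866 = 0.233
- f = 10%: p = 0.36; 0.0687 + 0.2319 = 0.301
- f = 25%: p = 0.30; 0.1176 + 0.3025 = 0.420

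P(keep) over a range of T:

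| T | f = 0 | f = 10% | f = 25% | f = 50% |
|---|---|---|---|---|
| 20% | 0.655 | 0.704 | 0.776 | 0.886 |
| 30% | 0.420 | 0.487 | 0.594 | 0.776 |
| 40% | 0.233 | 0.301 | 0.420 | 0.655 |
| 50% | 0.109 | 0.164 | 0.274 | 0.534 |

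The f = 0 column is also what the rule would give if events related to either drug counted. Each row rises from left to right, so the omission can only favour keeping the level.

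**The case against.** **The rule fits one of the two stated aims.** If the lead-in is about ipilimumab added to nivolumab, attributing DLTs to the added drug is a defensible design. Other passages support that view. Cohort 1 nivolumab is described as well tolerated (Section 2.4), recovered DLT patients may continue on nivolumab alone (Section 5.2.2), and failure at level -2 leads to nivolumab monotherapy (Section 5.2.1). This stands as far as it goes, so a reader should not infer that the lead-in cannot answer its stated question; that holds for only one of the two aims. It does not explain the wording of Section 5.2 or a table that lengthens both intervals. Cohort 1 also did not give nivolumab after protocol radiation.

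**The gap is narrow.** Possible relatedness to ipilimumab is a low bar, and Section 6 acknowledges that the two drugs' toxicities overlap. A reader might infer that all severe nivolumab toxicity is left out. The documents do not support that, because anything rated possible for both drugs counts.

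**Nivolumab as a concurrent medication.** A reader might infer that the Section 5.2.2 exclusion lets investigators blame nivolumab under that term. This is strained: Section 5.8 names both drugs as investigational products, and Section 5.9.4 separates concomitant medication from study drug. One clarifying sentence would close the matter.

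**There is a backstop.** Section 14.1.5.2 counts events related to any study treatment and suspends accrual at 2 of the first 10 patients, or above 20% thereafter. A grade 4 nivolumab infusion reaction would count there. But the rule covers only grade 4 or higher non-hematologic events, and it neither reaches grade 3 events nor feeds the choice of dose level.

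**The infusion case is an edge case.** A reaction before any ipilimumab says little about the interval between combination doses. It does show that the replacement rule can remove a severe event on the regimen from the 3+3 altogether.

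**Conclusion.** The point holds as an inconsistency of definition. Sections 5.2 and 5.2.1 state different aims and Table 5.2.1 changes both drugs, yet DLT attribution is to ipilimumab alone. What drops out is grade 3 or higher toxicity rated related to nivolumab and unlikely or unrelated to ipilimumab, together with any patient replaced after such an event without having received ipilimumab.

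The direction is certain and the size is not. Both T and f are assumptions, and if no event is attributed to nivolumab only, nothing changes. A reader might take the rise from 23% to 30% or 42% as an estimate of bias in this trial. It is only an illustration of sensitivity, because the documents give neither a true rate nor an attribution split. The calculation also leaves out replacement of patients. The inconsistency itself does not depend on these numbers and should be corrected.

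**What to change.** Reconcile Sections 5.2, 5.2.1 and 5.2.2 and Table 5.2.1 to one stated aim, then make four elements match it: DLT attribution, the radiation exclusion sentence, the concurrent-medication exclusion, and the evaluability and replacement rule.

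- If the aim is the combination, as Section 5.2 and the table indicate, DLT attribution should be to nivolumab and/or ipilimumab. A patient with such an event after the first dose of either drug should be evaluable and not replaced. The radiation sentence has to be edited at the same time. As it stands, it would still exclude an event possibly due to nivolumab, unlikely due to ipilimumab and probably due to radiation.
- If the aim is ipilimumab alone, Section 5.2 should say so. The plan should explain why both intervals change, and state how events attributed only to nivolumab are handled.
- In either case, say whether the other study drug can be a concurrent medication for the exclusion.

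The cost is amendment wording, since per-agent attribution is already collected under Section 7.2.6. The downside of counting either drug is that a level fails more often to the extent that nivolumab-only events occur. At an assumed 20% true rate, the chance of keeping the level would be 66%, against 70% (f = 10%) or 78% (f = 25%) under the current count. At 40%, failure would be 77%, against 70% or 58%.
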